For patients identified in the setting of a 3-vessel qualifying diagnostic angiogram and successful PCI of a non-LM or non-LAD vessels in the same or subsequent procedure, randomization into the trial must occur within 90 days following the initial qualifying angiogram. The first “study” intervention must be performed within 14 days following randomization (see above Table for possible procedure options).

Randomization will be stratified by center, PCI of non-LM or non-LAD vessels within the prior 90 days, and type of vessels treated (1) LAD and Diagonal only; 2) LAD (or Left Main) and LCX or RCA; 3) LAD (or Left Main) and both LCX and RCA). The randomization scheme will be in random blocks of 4 and 6 within each stratum to maintain balance.

Randomization will be generated centrally and performed through a Web-based data collection system that automates the delivery of the randomization codes. The treatment assignment will be

sent to the site coordinator electronically, in a secure fashion, and electronic verification of the treatment assignment will be required before proceeding with the treatment intervention. From that point on, primary efficacy will be analyzed by intention-to-treat; that is, the patients will be grouped by their assignment at randomization whether or not they actually received the treatment to which they were assigned.

MASKING

Neither patients nor investigators will be blinded to treatment assignment due to the nature of treatment interventions. Clinical and CCC investigators will, however, be blinded to all data from other clinical sites, except serious unexpected adverse events (SAEs) for IRB/REB reporting purposes. The DCC Research Nurse will be blinded to treatment assignment during follow-up telephone calls and will be blinded to aggregate outcomes data. MACCE events will be adjudicated by the independent CEC and trial oversight will be provided by an independent Data & Safety Monitoring Board (DSMB).

TREATMENT INTERVENTIONS

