The study will be conducted in between 50 and 125 U.S. and non-U.S. clinical sites with extensive experience in minimally invasive surgical coronary revascularization and multi-vessel PCI, as well as expertise in hybrid revascularization. The sites will be selected by the multi-disciplinary Hybrid Trial Steering Committee with particular focus on procedural expertise and evidence of a functioning multi-disciplinary heart team. An average recruitment of 98 patients monthly (2 patients/month/site) is anticipated.

Each clinical center will be required to obtain IRB/REB approval for the initial protocol and informed consent document and any subsequent revisions in a timely fashion, to recruit patients, to collect data and enter it accurately into the electronic data capture (EDC) system, to faithfully follow the protocol and adhere to the standards of Good Clinical Practice (GCP) and HIPAA or Personal Information Protection and Electronic Documents Act (PIPEDA) regulations. In addition, centers will be required to provide the DCC the information necessary for interim, annual, and final reports, to provide source documents, data and regulatory documents to study monitors, to respond promptly to DCC inquiries, and, to participate in analyses and reporting of study results.

Site Approval

The following documents are required for all sites approved to participate in the trial:

- Clinical Study Agreement with the CTSN DCC: InCHOIR, Department of Health Policy, Icahn School of Medicine at Mount Sinai
- Signed Conflict of Interest Statements
- Signed and dated CVs for all staff on Delegation of Authority Log
- Completed Delegation of Authority Log
- HIPAA/PIPEDA and Human Subjects/GCP training documentation (as required by local institutional guidelines) for all staff on Delegation of Authority Log
- Current licenses for all staff on Delegation of Authority Log
- IRB/REB roster
- IRB/REB approval for protocol, informed consent document, HIPAA authorization (US sites)
- NIH Stroke Scale Training Certification for appropriate staff
- Laboratory Normal Ranges
- Certification forms for Surgeons and Interventional Cardiologists
- Signed Document Approval Form for protocol
- Study-specific training documents

INVESTIGATORS

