A decision to stop the trial for safety reasons will be based on the result of the interim analysis as well as other supporting evidence that either arm of the trial poses unacceptable risk to patients. Should the data suggest that the composite rate of death, stroke or MI is significantly higher in one group than the other at the interim analysis (with a p-value of ≤ 0.0031), additional analyses and sub-group analyses will be conducted to supplement this information including investigation of site effects, adherence to the guideline-directed medical therapy, and other ad-hoc pertinent analyses as discussed and agreed upon with the DSMB.

Analysis Plan

The primary analysis will be an intent-to-treat analysis that will include all randomized participants regardless of treatment actually received or follow-up schedule. All hypothesis testing will be conducted using two sided tests at $\alpha = 0.05$.

Univariate Analysis

All outcome measures will be described in a univariate analysis. For continuous variables means and standard deviations will be calculated. For discrete and dichotomous variables, contingency tables will be used.

Analysis of Primary Endpoint

The primary endpoint of this study will be MACCE defined as all-cause mortality, myocardial infarction (MI), stroke, or unplanned revascularization over a minimum of 5 years of follow-up after randomization. Overall time to first event will be estimated using Kaplan-Meier curves. Survival time will be defined as the time (in months) between randomization and the occurrence of MACCE. To compare the HCR arm with the PCI arm we will use a stratified log-rank statistic using the stratification variables from the randomization procedure. A Cox proportional hazards model with treatment and stratification factors as covariates will be used for the multivariate analysis of the time to first MACCE. The assumption of proportionality will be tested prior to fitting the model. If the proportional hazards assumption is not met, the extended Cox model will be used. Hazard ratios and their 95% confidence intervals will be computed. Survival will be included in the analysis as censored if they are alive and free of

MACCE at the end of the study. Although we do not anticipate interactions between treatment and stratification factors, formal tests for interactions will be assessed using proportional hazards models.

Analysis of Secondary End-points

Secondary outcomes of the study will be analyzed as follows:

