Cardiovascular Events

Secondary cardiovascular events include MACCE at each data collection time point; individual components of MACCE (all-cause mortality, stroke, myocardial infarction, unplanned revascularization,); cardiovascular and non-cardiovascular mortality, ischemia-driven revascularization, and other cardiovascular events.

MACCE at each time point, individual components of MACCE, cardiovascular and non-cardiovascular mortality, , ischemia-driven revascularization other cardiovascular endpoints such as stent thrombosis and symptomatic graft stenosis or occlusion, and bleeding events will be analyzed using the stratified log-rank statistic in the manner of the primary outcome. Unplanned revascularization, stroke, MI, and cardiovascular mortality may not occur because death from any cause precedes the event, thus it is possible that censoring patients from all-cause mortality may lead to biased estimates when analyzing time to first event of these outcomes. As a sensitivity analysis, competing risks analysis using the methods of Gray²⁹ and Fine and Gray³⁰ will be used to calculate cause-specific cumulative incidence. Gray and Fine's test will be compared with the log-rank test for the treatment group effect, and the cumulative incidence curve will be compared to the Kaplan-Meier curve.

For unplanned and ischemia-driven revascularizations, a Poisson regression model will be used to assess differences in the rate of revascularization between groups. Time to death will be described by Kaplan-Meier curves and differences between randomization groups assessed via the stratified log-rank test. Mortality analyses will be conducted for both cardiovascular and non-cardiovascular mortality.

Hospitalizations

All cause and cardiovascular re-admissions will be recorded. A Poisson regression model will be used to compare the rate of readmission between groups for any cause, and specifically for cardiovascular hospitalizations.

Health Status

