Health status will be measured by Angina Score (Canadian Cardiovascular Society Classification [CCSC]) and by QoL surveys (SF-12 and EuroQOL). The distribution of CCSC angina class will be presented for each randomization arm and compared using a chi-squared test at each time point. Quality of life will be measured using the SF-12 and EuroQol. Quality of life will be analyzed longitudinally using mixed effects models.^{31, 32, 33} Log-transformations will be used, if necessary to normalize the variables or stabilize the variance. These models will be used to predict outcome given treatment group and time. The interaction between treatment and time will be used to determine the difference between the two arms over time.

Cost-effectiveness

A cost-effectiveness analysis will be performed from an overall healthcare system perspective. Costs associated with hospitalizations and outpatient services will be estimated from collected medical claim data using center-specific ratios of cost to charges. Multivariable imputation algorithms will be used to impute costs for patient-reported out of network MACCE related hospitalizations. Community-based health state preferences will be estimated from the trial's EuroQOL data using an algorithm developed for the U.S. general population.³⁴

We will subsequently develop an individual-level decision model, which will predict and extrapolate the overall survival, quality of life, and costs per trial participant as a function of randomization and MACCE. With the decision model we will compare the two scenarios: HCR vs. PCI by rerunning the randomized trial "in silico". In this re-simulated trial, each of the 2354 patients will be virtually exposed to both scenarios. Subsequently, each patient's life course according to an intention-to-treat principle is modeled by microsimulation while individualizing event rates, quality of life and costs.

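### The SF-12 and EuroQol mixed models are described without the randomization factors, which makes tests of arm differences in quality-of-life level slightly conservative

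*Combined protocol and SAP*

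**What the plan says.** Treatment Assignments sets the design: "Randomization will be stratified by center, PCI of non-LM or non-LAD vessels within the prior 90 days, and type of vessels treated". Vessel type has three levels, and "The randomization scheme will be in random blocks of 4 and 6 within each stratum to maintain balance".

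Analysis of Primary Endpoint carries the factors forward. For the main comparison "we will use a stratified log-rank statistic using the stratification variables from the randomization procedure", followed by "A Cox proportional hazards model with treatment and stratification factors as covariates". The Cardiovascular Events paragraph applies the same stratified test to the secondary time-to-event outcomes.

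The Health Status paragraph analyzes SF-12 and EuroQol longitudinally with mixed effects models and adds: "These models will be used to predict outcome given treatment group and time". It then names the treatment-by-time interaction as the way to judge the difference between arms over time. It mentions no stratification factor and does not say whether baseline quality of life is a response, a covariate or neither. The endpoint definition speaks of change from baseline.

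The revascularization and readmission rates get Poisson models described only as group comparisons, for example "A Poisson regression model will be used to compare the rate of readmission between groups for any cause". Nothing in the plan adds the strata to any of these models, and nothing excludes them.

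**The concern.** Blocked allocation within strata makes the arms nearly equal in center, recent PCI and vessel type. If these factors predict quality of life, the arm difference in level varies less from trial to trial than a model without them assumes. Such a model counts the between-stratum variation as error, so its intervals are too wide and its tests reject less often than 5% under the null.

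Health status and quality of life are the stated secondary objective, with assessments at 30 days and yearly to 60 months. The models are meant to predict outcome by arm and time, so arm differences in level are a natural thing to report from them. Some precision would be lost there although the factors are already recorded.

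**Working it through.** **Inputs from the documents.** N = 2354, 1:1 allocation, 15% loss, two-sided 0.05, 50 to 125 sites, two levels of recent PCI and three of vessel type. This gives 50 × 6 = 300 to 125 × 6 = 750 cells, or 2354/300 = 7.8 to 2354/750 = 3.1 patients per cell.

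**Inputs that are assumed.** The documents give no quality-of-life SD, within-patient correlation or variance share for the strata, and no quality-of-life sample size, so there is no figure of the plan to reproduce. I take a single-visit variance of 1, a within-patient correlation of 0.6, and strata explaining R² = 3%, 7% or 13% of single-visit variance. About 2000 patients contribute (2354 × 0.85 = 2001).

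**1. Level at one visit, baseline not in the model.** With allocation balanced within strata, the unadjusted SE is too large by k = 1/√(1 − R²). The true size is 2[1 − Φ(1.96k)]. Where the adjusted test has 80% power, the unadjusted power is Φ(2.802 − 1.96k).

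| R² | k | True size | Power |
|---|---|---|---|
| 3% | 1/√0.97 = 1.015 | 4.7% | 79% |
| 7% | 1/√0.93 = 1.037 | 4.2% | 78% |
| 13% | 1/√0.87 = 1.072 | 3.6% | 76% |

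Simulation agrees, with a slightly smaller gain because blocks are incomplete and center effects must be estimated:
- 60 centers, 1500 runs, 13% explained: SE 0.0446 without strata and 0.0419 with them (ratio 1.064), size 4.0%. At 3% explained the SE is about 1% larger.
- 50 to 125 unequal centers, 2000 patients, 13% explained: SE 5 to 9% too large, size 3.3 to 3.8%, power 75 to 76% against 78 to 80% adjusted. At 7% explained, power is 77 to 79% against 79 to 81%.

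**2. Level averaged over visits.** Averaging removes visit noise but not the strata, so their share grows. Simulation used 2354 patients, 50 centers, seven time points, 15% loss, a random patient intercept and 150 runs per setting:
- Strata explain 10% of between-patient variance (0.10 × 0.6 = 6% of single-visit variance): SE 0.03373 falls to 0.03223, ratio 1.047.
- Strata explain 20% (0.20 × 0.6 = 12%): SE 0.03373 falls to 0.03059, ratio 1.103.

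**3. Level at one visit with baseline as covariate.** Baseline already carries part of the stratum effect. Without strata the residual variance is 1 − 0.6² = 0.64. With strata it is (1 − R²) − (0.6 − R²)²/(1 − R²):
- R² = 3%: 0.97 − 0.57²/0.97 = 0.635, SE ratio √(0.64/0.635) = 1.004.
- R² = 7%: 0.93 − 0.53²/0.93 = 0.628, ratio 1.010.
- R² = 13%: 0.87 − 0.47²/0.87 = 0.616, ratio 1.019.

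**4. Change from baseline.** The strata do not change over time, so constant stratum effects cancel. The variance of a change is 2(1 − 0.6) = 0.8 whatever R² is, and the SE is √(4 × 0.8/2000) = 0.0400. Simulation at 13% explained gives 0.0400 without strata and 0.0402 with them.

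**5. Treatment-by-time interaction.** In the simulation of step 2 the SE is 0.00585 without strata. With them it is 0.00585 (10% of between-patient variance) or 0.00584 (20%).

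**The case against.** The strongest objection is that the plan's named comparison is the interaction, and the endpoint definition is change from baseline. Both are within-patient contrasts, and steps 4 and 5 show that adding the strata as main effects does nothing for either. This stands. Only stratum-by-time terms could matter there, and only if trajectories differ between strata. What remains is the arm-by-visit and average levels that the models are said to predict.

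A reader might also infer that the Poisson models lose precision in the same way. They do not. The SE of the log rate ratio is about √(1/E1 + 1/E0), where E1 and E0 are the event counts in the two arms, with or without strata. In simulation with an assumed 0.06 events per patient-year it was 0.0785 unadjusted and 0.0787 adjusted. With stronger stratum effects it was 0.0781 and 0.0784. Unplanned and ischemia-driven revascularization also have a stratified log-rank test. The Poisson sentences are brief and silent on covariates, which is not the same as excluding them.

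Two further objections have some weight. The variance shares are assumed, and at 3% the effect is negligible. The error is conservative, so it cannot create a false positive. Finally, the simulation of averaged levels fitted center as a fixed effect. A random intercept should give nearly the same SE when arms are balanced within center, but it was not simulated there.

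**Conclusion.** The point holds for one class of results: arm differences in SF-12 or EuroQol level, at a visit or averaged over visits.

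- If the strata explain 3 to 7% of single-visit variance, the SE is about 1 to 4% too large for one visit and about 5% for an average (the latter simulated at 6%).
- At 12 to 13% it is about 7% too large for one visit and about 10% for an average.
- With baseline as covariate, the one-visit excess at 13% shrinks to about 2%.
- In power, the single-visit cost is 1 to 4 points from 80%.

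All of this rests on the assumed variance shares and, for the averaged and baseline-adjusted results, on the assumed within-patient correlation of 0.6.

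A reader might infer that the planned quality-of-life test itself is miscalibrated or underpowered. The documents do not support that, because the named interaction is essentially unaffected. The primary analysis and its sample size are not touched. This is a free improvement of low priority, for secondary endpoints only.

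**What to change.** In the Health Status paragraph, state that the SF-12 and EuroQol models include treatment, time, treatment by time, recent PCI (yes/no) and vessel type (three levels) as fixed effects, with a random intercept for center in addition to the patient random effect. State how baseline quality of life enters. State that arm differences at each visit will be reported from this model.

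Enter the factors as main effects rather than as fully crossed cells, since those would hold only about 3 to 8 patients each. In a linear model the added terms leave the meaning of the treatment effect unchanged, and fixing them in advance removes a later choice between adjusted and unadjusted results.

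The cost is a change of wording in the analysis plan. The factors are known at randomization and no new data are needed.

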The ***secondary objectives*** are to determine the impact of HCR compared to PCI on health status and quality of life.

BACKGROUND AND SIGNIFICANCE

Importance of the Study

The increasing prevalence of coronary artery disease (CAD), advances in coronary artery bypass grafting (CABG), PCI, and concomitant medical therapy, and the costs of revascularization have resulted in rising interest regarding the appropriate indications and alternatives for coronary revascularization. The 2009 ACCF/SCAI/STS/AATS/ AHA/ASNC Appropriateness Criteria for Coronary Revascularization document that for patients with 3-vessel disease requiring revascularization, CABG is rated as appropriate while revascularization by PCI is rated as uncertain.¹ Moreover, the recent SYNTAX trial demonstrated that CABG was superior to PCI with first generation drug eluting stents (DES) for patients with 3- vessel disease and/or left main coronary artery (LM) disease.² However, the SYNTAX trial results were driven by the repeat revascularization component of the primary composite endpoint (lower for CABG), and divergence with the outcomes of the stroke component (higher for CABG) has led to differences in interpretation of the overall results.

These differences in interpretation, coupled with strong patient preferences for the lower level of invasiveness, a potentially lower stroke risk, and faster recovery have driven the widespread adoption of PCI. At the same time, CABG has been shown to provide improved long-term durability, superior long term symptom relief, fewer repeat interventions and higher rates of survival.²⁻⁴ Integrating the positive features of both PCI and CABG has been the fundamental rationale of “hybrid” coronary revascularization.

Hybrid coronary revascularization is the intended combination of CABG and PCI. The HCR strategy combines grafting of the left anterior descending artery (LAD) coronary artery using the left internal mammary artery (LIMA) and PCI of non-left anterior descending coronary artery (LAD) coronary stenoses. Essentially, stents are substituted for saphenous vein grafts (SVG) for non-LAD lesions, and the surgical LIMA to LAD bypass is performed, ideally through a limited access, minimally traumatic approach. The rationale for choosing HCR over PCI or CABG alone stems from a number of observations:

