The change in quality of life (QOL) from baseline will be measured, using the Short Form-12 (SF-12) general health status index and EuroQol 5-D (EuroQoL) which measures health state preference from the individual and societal perspective. The SF-12 instrument examines 8 quality of life dimensions (physical activity, social activity, role/physical, body pain, general mental health, role/emotional, vitality and general health perception). The EuroQoL 5-D is a standardized instrument for measuring health-related quality of life. This questionnaire provides a simple descriptive profile that consists of 5 dimensions. The 5 domains are anxiety/depression, pain/discomfort, usual activities, self-care, and mobility. The instrument also has a self-assessment of health status.
- *Cost-effectiveness*
Cost-effectiveness will be evaluated using a microsimulation model, which will predict the accrued health care costs and quality-adjusted life expectancy for each subject at the end of the trial follow-up period and in addition over a lifetime horizon.

For this trial, the SF-12 is available in English, Spanish and French, and the EuroQol is available in English and French. Inability to read and complete these instruments in the available languages does not preclude a patient from enrollment in the trial (a family member may assist in completing the QOL questionnaires). Copies of these instruments can be found in Appendix II.

UNANTICIPATED ADVERSE DEVICE EFFECTS

Reporting of Serious Adverse Events and Unanticipated Adverse Device Effects

All unanticipated adverse device effects (UADEs) must be reported to the DCC and the clinical center's IRB/REB within 24 hours of knowledge of the event.

The DCC will notify the NHLBI program officer of any UADEs via e-mail within 24 hours of receipt of the event. The program officer will report these events to the DSMB chair within 72 hours of notification.

DCC Reporting to FDA

The DCC will report UADEs to FDA according to Code of Federal Regulations 21CFR812.150 for this Investigational Device Exemption (IDE) trial.

CLINICAL CENTERS

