Data extracted from UHC database and UB forms for all hospitalizations required to complete the original planned revascularization strategy (if staged)

Medical costs are defined as hospital costs and physician fees incurred during the index revascularization procedure(s) and hospitalization. Cost data will be extracted from the UHC operational database system for member sites, and from UB medical claims forms for sites without UHC membership. Dates of charges and revenue codes will be used to match the cost data with data on study-procedure related hospitalization from the STS registry. UB medical claims will be converted to costs using the same methodology as used by UHC to estimate costs including center-specific ratios of cost to charges. These ratios will be based on the annual Medicare costs reports submitted annually by participating study sites to Medicare. Physician fees will be based on collected length of stay data and the Medicare fee schedule. Physician fees for HCR and PCI procedures will include those for the primary surgeon, surgical assistant, and anesthesiologist. Non procedure-related physician fees regarding the index hospitalization(s) will be based on collected length of stay data and the Medicare fee schedule. The patient-specific cost data downloaded from the UHC operational database system and electronic UB data will be de-identified and coded with the unique study ID, and subsequently transferred by the participating clinical site to the DCC via a secure FTP website.

Post-Intervention Site Activities

Follow-up must be performed at 30 (± 7) days following all procedures (index and staged) that occur within 90 days of the first study revascularization procedure.. However, if a staged procedure occurs <45 days after the first procedure, it will not be considered a protocol violation if a 30-day follow-up visit was not performed after the first procedure.

Medications

This form captures medication use, including antiplatelet and anticoagulant agents, beta blocker, and ACE inhibitors, ARBs, aldosterone antagonists and statins.

Angina Class - Canadian Cardiovascular Society Classification (CCSC)

The presence of angina will be assessed, and when present, classified according to the CCSC

Quality of Life

The SF-12 and EuroQol (Appendix II) questionnaires will be completed by the patient to assess quality of life.

MACCE and Other Cardiovascular and Bleeding Events

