At 6 (± 1), 12 (± 1), 18 (± 1), 24 (± 1), 30 (± 1), 36 (± 1), 42(± 1), 48 (± 1), 54 (± 1), and 60 (± 1) months post-randomization, via centralized DCC telephone follow-up (when allowed by local

The presence of angina will be assessed by the DCC research nurse, and when present, classified according to the CCSC scale and documented on this form. CCSC classification scheme is detailed in Appendix I.

Quality of Life

At 12 (±1), 24 (±1), 36(±1), 48 (±1), and 60 (±1) months post-randomization, via centralized DCC telephone follow- up (when allowed by local IRB/REBs)

The SF-12 and EuroQoL will be administered annually, either by phone from the DCC research nurse or site coordinator, or via electronic patient portals, including electronic QoL surveys that can be utilized for all patients with computer, tablet or smart phone capability. The electronic forms will also be accessible for patient reporting via a password protected portal on the HCR Trial website.

Costs

Collected at 12 (±1), 24 (±1), 36 (±1), 48 (±1), and 60 (±1) months post-randomization, via electronic transfer from UHC database and UB forms

Medical costs were defined as hospital costs, physician fees, outpatient procedure costs, the cost of prescription drugs, and the cost of rehabilitation incurred after the index hospitalization. Medical claims associated with any hospital stay and outpatient service in participating sites are collected annually. Cost data will be extracted from the UHC operational database system for member sites, and from UB medical claims forms for sites without UHC membership. UB medical claims will be converted to costs using the same methodology as used by UHC to estimate costs using center-specific ratios of cost to charges. These ratios will be based on the annual Medicare costs reports submitted by participating study sites to Medicare. Multivariable imputation algorithms will be used to impute costs for patient-reported out of network hospital stays. Physician fees will be based on collected MACCE and length of stay data and the Medicare fee schedule. Resource use associated with prescribed medication and the rehabilitation of myocardial infarction and stroke will be estimated based on patient-reported information and will be converted into dollars using reimbursements from Centers for Medicare and Medicaid Services costing reports

Event Driven Data Collection

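### Quality of life is compared only through an unspecified treatment-by-time interaction, which is weaker than a direct contrast for a small stable benefit and cannot show whether a difference lasts

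*Combined protocol and SAP*

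**What the plan says.** The Objectives section makes QoL a named purpose of the trial: the secondary objectives "are to determine the impact of HCR compared to PCI on health status and quality of life". Under Definitions and Measurement of Endpoints, the Quality of Life entry says "The change in quality of life (QOL) from baseline will be measured", using the SF-12 and EuroQoL.

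The Health Status paragraph of the Analytical Plan says "Quality of life will be analyzed longitudinally using mixed effects models" and "These models will be used to predict outcome given treatment group and time". It then gives the only between-arm comparison for QoL: "The interaction between treatment and time will be used to determine the difference between the two arms over time". It names no treatment main effect, post-baseline average or difference at a given visit. The same paragraph compares angina class separately at each visit.

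The Data Collection Schedule places QoL at baseline, at 30 days after intervention, and at 12, 24, 36, 48 and 60 months. After the 30-day visit, "The SF-12 and EuroQoL will be administered annually".

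**The concern.** A treatment-by-time interaction asks whether the gap between arms changes from one time to another. Whether that also tests for a treatment difference depends on whether baseline is one of the times.

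If baseline sits inside the outcome (change scores), only follow-up visits are compared with each other. A benefit that appears by 30 days and stays the same size then gives an interaction of zero. If baseline is a time level and raw scores are modelled, the same benefit does produce an interaction. The test then spreads over six degrees of freedom, or is forced into a straight line that fits a step change poorly.

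One arm has thoracic surgery and the other does not, and the first QoL visit falls at 30 days. A short-lived early difference is therefore plausible, and it also produces an interaction. The stated test could thus be significant for a temporary or a lasting difference, or not significant despite a lasting one. The conclusion on a named secondary objective would rest on modelling choices that the plan leaves open.

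**Working it through.** The documents give no QoL power figure, so there is nothing to reproduce. The check compares the tests that the text permits.

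**Inputs from the documents.** There are 2354 patients allocated 1:1, so 1177 per arm. Loss to follow-up is 15% by the end of the study, and 1177 × 0.85 ≈ 1000 per arm. Tests are two-sided at 0.05. Times are 0, 1, 12, 24, 36, 48 and 60 months; month 1 stands for the 30-day visit, which is counted from the procedure.

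**Assumptions.** SD is 1 at every visit, within-patient correlation ρ is exchangeable at 0.5 or 0.7, and data are complete at n = 1000 per arm. The effect δ is 0.10 or 0.15 SD. Power comes from a noncentral chi-square with noncentrality λ.

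**1. Change from baseline as outcome.** With a constant benefit, all six follow-up differences are equal. Every contrast among them is zero, so λ = 0 and rejection is 5% for linear or categorical time at any n or ρ. A simulation at 0.20 SD (2000 trials, ρ = 0.5) rejected in 4.3% (categorical) and 5.1% (linear).

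**2. Raw scores, baseline as a level, categorical time (6 df).** λ = [n / (2(1−ρ))] × Σ(d_j − d̄)², where d_j is the arm difference at time j. A constant benefit differs from zero at six of seven times, so Σ(d_j − d̄)² = (6/7)δ².
- δ = 0.10: λ = 1000 × 0.857 × 0.01 = 8.57 (ρ = 0.5), power 56.5%; λ = 1667 × 0.857 × 0.01 = 14.29 (ρ = 0.7), power 82%.
- δ = 0.15: λ = 19.29 and 32.14, power 93.1% and 99.6%.

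**3. Raw scores, baseline as a level, linear time (1 df).** λ = [n / (2(1−ρ))] × [Σ(t_j − t̄)d_j]² / Σ(t_j − t̄)². Here t̄ = 181/7 = 25.86 and Σ(t_j − t̄)² = 7921 − 181²/7 = 3240.9. For a constant benefit the ratio is δ² × 25.86²/3240.9 = 0.2063δ².
- δ = 0.10: λ = 2.06 and 3.44, power 30% and 46%.
- δ = 0.15: λ = 4.64 and 7.74, power 58% and 79%.

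**4. Baseline-adjusted average over months 12 to 60.** Variance = (2/n)[(1+4ρ)/5 − ρ²], which is 0.00070 (ρ = 0.5) or 0.00054 (ρ = 0.7).
- δ = 0.10: z = 0.10/0.0265 = 3.78 and 0.10/0.0232 = 4.30, power 97% and 99%.
- δ = 0.15: z = 5.67 and 6.45, power about 100%.

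**5. A difference at 30 days only.** Under the model in step 2, one of seven times differs from the rest, so Σ(d_j − d̄)² is again (6/7)δ². At 0.15 SD, λ is again 19.29 and 32.14, and power is 93.1% and 99.6%: exactly the values for the lasting benefit. With change scores the same 30-day difference gives significance in 80 to 95% (linear) or 94 to 99.7% (categorical) of trials. The month 12 to 60 contrast stays at 5%.

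| Test (ρ = 0.5 to 0.7) | Constant 0.10 SD | Constant 0.15 SD | 0.15 SD at 30 days only |
|---|---|---|---|
| Interaction, change score, linear | 5% | 5% | 80–95% |
| Interaction, change score, categorical | 5% | 5% | 94–99.7% |
| Interaction, raw with baseline, linear | 30–46% | 58–79% | 54–76% |
| Interaction, raw with baseline, categorical | 56.5–82% | 93–99.6% | 93–99.6% |
| Baseline-adjusted average, months 12–60 | 97–99% | about 100% | 5% |

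**The case against.** The strongest reply is that the plan never says change scores are modelled. The endpoint entry says what is measured; the analysis paragraph leaves the dependent variable open. It also allows log-transformation, which suits raw scores better, since a change score can be zero or negative. With raw scores and baseline as a time level, the interaction does test for a between-arm difference in change from baseline, and the two sections agree. Power for 0.15 SD with categorical time is then 93% or more. This stands. A reader might infer that the planned test has no power for a stable benefit; the documents do not support that as a general statement, because it holds only under the change-score reading.

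A reader might also infer that significance driven by the 30-day visit is a false positive. It is not. Thirty days is a listed secondary-endpoint time, faster recovery is part of the trial's rationale, and the objective is not limited to lasting effects. Such a result would correctly show different time courses. What remains is that it would not show a lasting difference.

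Model predictions by arm and time, descriptive means and SDs, and the confidence interval for the QALY difference would give some sense of direction. This mitigates only in part. None is named as the QoL comparison, and the QALY result is a simulation output built on EuroQoL that does not test the SF-12.

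**Conclusion.** The concern holds as one of specification and choice of test. Under every reading tried, the interaction has less power for a constant 0.10 SD benefit than a direct contrast: 5%, 30 to 46%, or 56.5 to 82%, against 97 to 99%. For 0.15 SD under the most favourable reading the gap is small: 93 to 99.6% against about 100%. Even then the omnibus test has no direction and gives the same power for a lasting benefit as for an equal difference at 30 days only.

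These figures rest on my assumed effect sizes, correlations, exchangeable structure and complete data at 1000 per arm. Two results do not depend on the effect sizes chosen: the 5% rejection with change scores, and the equality of the lasting and 30-day-only cases under the categorical model.

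The plan should be changed, since QoL is a named secondary objective. The primary endpoint and the interim safety rule are not affected, and the plan attaches no power claim or success criterion to QoL.

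**What to change.** In the Health Status paragraph of the Analytical Plan:

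- Specify a mixed model with categorical visit and the baseline score as a covariate, or with baseline means constrained equal across arms.
- Name one treatment contrast as the QoL test, for example the average difference over months 12 to 60 or over all post-baseline visits.
- Report visit-specific differences, including 30 days, with 95% confidence intervals.
- Keep the treatment-by-time interaction as a description of time course.

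This is a wording change that uses the same data and model family. There is one small cost: an average over months 12 to 60 leaves early recovery out of the single test, so the 30-day difference must be reported beside it.
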